11.4. Patients Included in Analysis

Analysis populations

Safety evaluation: Randomized patients will be included in the safety evaluation.

Efficacy evaluation: The full analysis set (FAS) defined in Section 11.3 will be used.

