7. EXPECTED ADVERSE EVENTS

An adverse event (AE) is defined as any undesirable medical event that occurs in a patient receiving the study drug (excluding worsening of the primary disease). These events may or may not have a clear causal relationship with the study drug. Essentially, an adverse event is any undesirable or unintended sign (including abnormal laboratory test values), symptom, or condition that arises in a patient receiving the study drug, regardless of whether the event has a causal relationship with the study drug. In this study, adverse events that satisfy the above definition will be identified and recorded on case report forms.

If the grade according to the Japanese translation of CTCAE v4.0 worsens, the change will be reported as an adverse event on a case report form. This may also apply to changes within reference ranges or grades if the site investigator believes the event merits clinical consideration (including changes in test values).

The causality of adverse events will also be recorded on case report forms. The Japanese

translation of CTCAE v4.0 will be used for coding adverse events.

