10.3. Definitions of Analysis Populations

The analysis populations for regular monitoring and final analysis are defined as follows.

All enrolled patients

The “all enrolled patients” population consists of all patients enrolled in accordance with **Section 5.1. Enrollment and Randomization Procedures** excluding duplicate enrollments and erroneous enrollments.

Ineligible patients

The “ineligible patients” population consists of enrolled patients who did not meet the eligibility criteria (ineligibility was discovered at a later date) or were unable to start the protocol treatment.

All eligible patients

The “all eligible patients” population consists of all enrolled patients except patients determined to be ineligible by the research group. Patients judged to be ineligible at the sole discretion of an investigator, site coordinator, or lead site investigator are included in “all eligible patients”. In order for the research group to judge a patient ineligible, the chair of the research group must approve the designation during the final analysis. For analysis for regular monitoring or when presenting data at an academic conference before submission of the final analysis report, the data center may choose to not include patients judged to be ineligible by the study coordinator with the understanding of the study coordinator.

Full analysis set

The full analysis set consists of all enrolled patients who completed the protocol treatment in whole or in part. Patients who did not start the protocol treatment at all are considered “untreated patients”.

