11.6.2. Secondary endpoints

Progression-free survival (PFS)

The length of time from the date of randomization until diagnosis of recurrence or death from any cause, whichever is sooner.

Time to progression (TTP)

The length of time from the date of randomization until diagnosis of progression (PD) by the modified RECIST criteria. The date on which the investigator evaluates a patient and performs tests will be considered the date of progression as assessed by imaging. In the case of clinical progression, the date of the examination in which clear evidence of disease progression was observed will be considered the date of progression. Investigators will record the date progression was diagnosed and the reason on medical records. Patients whose disease does not progress as of the final follow-up point will be censored by the later of the last examination date and the last imaging test date for analysis. Patients who die before disease progression will be censored if the death was clearly unrelated to hepatocellular carcinoma or was due to rupture of gastroesophageal varices.

Overall response rate (ORR):

Will be determined using the modified RECIST criteria. Assessments will be made based on changes in the diameter of surviving tumors deemed viable by a modality such as contrast CT that are observed until completion or discontinuation of the protocol treatment.

Tumor markers:

Associations of baseline tumor marker levels and changes from baseline with efficacy will be explored.

Safety:

The Japanese translation of CTCAE v4.0 will be used to tabulate data for the safety population. The incidence and causality of each adverse event and serious adverse event will be tabulated by group and by CTCAE v4.0 grade. Blood pressure and other safety parameters will also be tabulated descriptively.

OS by tumor markers

Overall survival will be compared by tumor marker levels (AFP, AFP-L3, and PIVKA-II).

OS by Vp

Overall survival will be compared by Vp stage.

OS by response

OS will be compared between responders and non-responders

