12.2. Enrollment Period and Follow-up Period

Enrollment period: **45 months**, Follow-up period: 12 months

Initially, the study was started in October 2010 with a planned enrollment period of 24 months. However, the actual pace of enrollment was slower than expected, so the enrollment period was extended by one year in January 2012. As of August 2013, 180 patients (94.7%) have enrolled. Many patients have been unable to start the protocol treatment. Therefore, upon consultation with the research group, it was decided to extend the enrollment period, which was to conclude at the end of September 2013, by 9 months to the end of June 2014.

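### The safety set counts randomised patients who never started treatment, so adverse event incidence is understated by each arm's untreated share

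*Protocol*

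**What the plan says.** Section 11.4 fixes the safety population in one sentence: "Safety evaluation: Randomized patients will be included in the safety evaluation". It sets no condition of exposure, and no other section narrows it. Section 11.6.2 then uses that population: "The incidence and causality of each adverse event and serious adverse event will be tabulated by group and by CTCAE v4.0 grade".

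The protocol already recognises patients without exposure. The definitions of analysis populations (printed as 10.3, cited elsewhere as 11.3) say: "The full analysis set consists of all enrolled patients who completed the protocol treatment in whole or in part". Those who never start are named there as a separate, untreated category and fall outside the full analysis set. Section 11.4 uses the full analysis set for efficacy but not for safety.

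Two further places matter:

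- Section 7 defines an adverse event as "any undesirable medical event that occurs in a patient receiving the study drug", leaving out worsening of the primary disease.
- Section 12.2 reports 180 patients enrolled by August 2013, adds that "Many patients have been unable to start the protocol treatment", and gives this when explaining the nine-month extension of enrolment.

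**The concern.** An incidence is meaningful only if everyone in the denominator could have been counted in the numerator. Here the numerator is limited to people receiving study drug and the denominator is not. The protocol itself says that non-starters are numerous, so the mismatch is not hypothetical.

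Safety is a named secondary endpoint, and the tables by group are what a reader would use to weigh added infusion toxicity against any survival gain. Including unexposed patients is anti-conservative for harm because it lowers the reported rate. If the untreated share differs between arms, it also distorts the comparison.

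**Working it through.** The protocol states no figure for the safety set, so there is none to reproduce. The check has two parts.

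**1. Do the provisions combine as described?**

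- Denominator: all randomised patients (11.4).
- Numerator: events in patients receiving study drug (7).
- Non-starters are randomised patients. Under Section 5.2 the enrolment number and the assigned treatment are issued together, and under Section 6.1 the first cycle may begin up to 28 days after randomisation in both arms.
- Data collection is consistent with this. On-study signs and symptoms are collected by treatment cycle (8.2), and deaths of never-treated patients are outside expedited reporting (10.1.1).

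**2. How large is the effect?**

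Let p be the incidence in treated patients of an arm and d its untreated share. With no countable event in untreated patients:

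reported incidence = p × (1 - d)

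The planned size is 95 per arm (12.1). The protocol does not give d, so the non-starter counts below are assumptions.

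| Non-starters of 95 | d | Factor (1 - d) |
|---|---|---|
| 5 | 5.3% | 0.947 |
| 9 | 9.5% | 0.905 |
| 14 | 14.7% | 0.853 |
| 19 | 20.0% | 0.800 |

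For an assumed p of 40%:

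- d = 5%: 0.40 × 0.95 = 38%
- d = 10%: 0.40 × 0.90 = 36%
- d = 15%: 0.40 × 0.85 = 34%
- d = 20%: 0.40 × 0.80 = 32%

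*Equal d in both arms.* The factor cancels from the risk ratio and multiplies the risk difference. For assumed rates of 40% and 30% with d = 5% in each arm, the difference is 0.40 × 0.95 - 0.30 × 0.95 = 9.5 points instead of 10.0. The ratio stays at 1.33.

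*Unequal d, equal true rates.* With 40% in both arms and d of 15% and 5%, the table reads 34% and 38%. That is a false 4-point advantage for the arm with more non-starters, and a ratio of 0.34 / 0.38 = 0.895.

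*Unequal d, different true rates.* Take 40% for combination and 30% for monotherapy:

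| d combination | d monotherapy | Reported rates | Difference (true 10.0) | Ratio (true 1.33) |
|---|---|---|---|---|
| 10% | 5% | 36.0% vs 28.5% | 7.5 points | 1.26 |
| 15% | 5% | 34.0% vs 28.5% | 5.5 points | 1.19 |
| 20% | 5% | 32.0% vs 28.5% | 3.5 points | 1.12 |
| 5% | 15% | 38.0% vs 25.5% | 12.5 points | 1.49 |

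The last row reverses the imbalance (0.40 × 0.95 = 38.0%; 0.30 × 0.85 = 25.5%). The excess is then overstated, so the direction of the between-arm error depends on a split that the protocol does not give.

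With a treated-only denominator the reported rate equals p for any d.

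**The case against.** The best defence of a randomised safety set is that harm can precede the first dose. Section 7.2 expects complications of catheterisation before treatment begins, and a set restricted to dosed patients could lose them. That stands as a reason to keep patients with attempted reservoir placement and to list events in never-treated patients. It does not justify using all randomised patients as the denominator for drug event rates. As Section 7 is worded, such events would not count anyway in someone who never receives drug.

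It can also be said that Section 7.4 asks sites to watch for events throughout the study, so some events in untreated patients might be recorded. If their incidence were q, the shortfall would be d × (p - q) instead of d × p. That is smaller, but still an understatement whenever q is below p.

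The consequence is limited. Safety is secondary, Section 11.6.2 specifies tabulation and no formal test, and the overall survival comparison does not use this set.

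Three stronger readings are tempting, and the protocol does not support them:

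- A reader might infer that the combination arm has more non-starters because it needs a reservoir, so that its toxicity is masked. Section 12.2 gives no count and no split by arm. Section 6.1 sets the same 28-day window for both arms. Section 6.1.1 also allows sorafenib before infusion, so a combination patient whose placement fails may already have started treatment.
- A reader might infer that combination patients given only sorafenib will be tabulated as exposed to infusion. Section 11.6.2 says by group and does not say whether this means assigned or received. That detail may properly sit in the statistical analysis plan.
- A reader might conclude that tables should be regrouped by infusion received. Since sorafenib may come first, this would move combination patients with early harm into the sorafenib-only column, on the basis of something that happened after randomisation.

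**Conclusion.** Section 11.4 is wrong as written on this point. In any arm with untreated patients, incidence is understated by the factor (1 - d). This follows from Sections 7 and 11.4 together, and Section 12.2 shows that non-starters exist.

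The size is not known. For an assumed d of 5% to 20%, a 40% rate reads 38% to 32%. The effect on the between-arm comparison ranges from none on the risk ratio, when d is equal, to several percentage points on the difference, when it is not. It always favours the arm with more non-starters, and which arm that is cannot be told from the protocol. The event rates used here are illustrations and are not protocol figures. The calculation also assumes that untreated patients contribute no events, which is how Section 7 reads.

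The matter should be corrected, but it does not threaten the primary analysis.

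**What to change.** In Section 11.4, replace the safety sentence with a definition along these lines: the safety set comprises randomised patients who received at least one dose of any protocol drug or, in the combination arm, had reservoir placement attempted. In addition:

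- keep the randomised groups for the main safety tables;
- report the number of never-treated patients in each arm;
- list any events in never-treated patients separately;
- align the adverse event definition in Section 7 so that events from an attempted placement count even if no drug follows. Otherwise those few patients would recreate the same mismatch.

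The cost is a change of wording and of table denominators, plus confirmation from sites of whether placement was attempted in combination patients who were never dosed. Sample size and conduct of treatment are unaffected. The downside is that reported incidences become somewhat higher.

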11.5. Subgroup Analysis

Stratified analysis by average and total sorafenib dose will also be performed.

11.6. Endpoint Definitions

11.6.1. Primary endpoint

Overall survival (OS)

The length of time from the date of randomization until death from any cause. The date survival was last confirmed will be used to censor surviving patients. Unfollowable patients will be censored by the date survival was last confirmed before they became unfollowable.

11.6.2. Secondary endpoints

Progression-free survival (PFS)

The length of time from the date of randomization until diagnosis of recurrence or death from any cause, whichever is sooner.

Time to progression (TTP)

The length of time from the date of randomization until diagnosis of progression (PD) by the modified RECIST criteria. The date on which the investigator evaluates a patient and performs tests will be considered the date of progression as assessed by imaging. In the case of clinical progression, the date of the examination in which clear evidence of disease progression was observed will be considered the date of progression. Investigators will record the date progression was diagnosed and the reason on medical records. Patients whose disease does not progress as of the final follow-up point will be censored by the later of the last examination date and the last imaging test date for analysis. Patients who die before disease progression will be censored if the death was clearly unrelated to hepatocellular carcinoma or was due to rupture of gastroesophageal varices.

Overall response rate (ORR):

Will be determined using the modified RECIST criteria. Assessments will be made based on changes in the diameter of surviving tumors deemed viable by a modality such as contrast CT that are observed until completion or discontinuation of the protocol treatment.

Tumor markers:

Associations of baseline tumor marker levels and changes from baseline with efficacy will be explored.

Safety:

The Japanese translation of CTCAE v4.0 will be used to tabulate data for the safety population. The incidence and causality of each adverse event and serious adverse event will be tabulated by group and by CTCAE v4.0 grade. Blood pressure and other safety parameters will also be tabulated descriptively.

OS by tumor markers

Overall survival will be compared by tumor marker levels (AFP, AFP-L3, and PIVKA-II).

OS by Vp

Overall survival will be compared by Vp stage.

OS by response

OS will be compared between responders and non-responders

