3.2. Tumor Assessment

Tumor response will be assessed using version 1.0 of the modified RECIST criteria (mRECIST) [1]. Assessments will be made based on changes in the diameter of surviving tumors deemed viable by a modality such as contrast CT that are observed until

completion or discontinuation of the protocol treatment.

At the time of enrollment for this study (before treatment), the 5 largest tumors among intrahepatic lesions with a large maximum diameter will be selected as target lesions. Lesions other than the target lesions will be included as non-target lesions, and the largest 5 of those will be selected and evaluated.

However, observation of a new intrahepatic lesion will not be considered PD in this study. Determinations of the best overall response will not require confirmation.

Table 2 Assessment of Target Lesion Response: Conventional RECIST and mRECIST Assessment for HCC Following the AASLD-JNCI Guideline

RECIST	mRECIST for HCC
CR = Disappearance of all target lesions	CR = Disappearance of any intratumoral arterial enhancement in all target lesions
PR = At least a 30% decrease in the sum of diameters of target lesions, taking as reference the baseline sum of the diameters of target lesions	PR = At least a 30% decrease in the sum of diameters of viable (enhancement in the arterial phase) target lesions, taking as reference the baseline sum of the diameters of target lesions
SD = Any cases that do not qualify for either partial response or progressive disease	SD = Any cases that do not qualify for either partial response or progressive disease
PD = An increase of at least 20% in the sum of the diameters of target lesions, taking as reference the smallest sum of the diameters of target lesions recorded since treatment started	PD = An increase of at least 20% in the sum of the diameters of viable (enhancing) target lesions, taking as reference the smallest sum of the diameters of viable (enhancing) target lesions recorded since treatment started

AASLD, American Association for the Study of Liver Diseases; JNCI, Journal of the National Cancer Institute; HCC, hepatocellular carcinoma; mRECIST, modified Response Evaluation Criteria in Solid Tumors; CR, complete response; PR, partial response; SD, stable disease; PD, progressive disease.

Table 3 Overall Response Assessment in mRECIST: Responses for All Possible Combinations of Tumor Responses in Target and Nontarget Lesions with or without the Appearance of New Lesions

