6. TREATMENT PLANS AND CRITERIA FOR ADJUSTING TREATMENT

6.1. Protocol Treatments

6.1.1. Low-dose FP and sorafenib group (combination therapy group) (Table 1)

This study will use the following doses demonstrated as safe in a phase I/II study of sorafenib and low-dose cisplatin/fluorouracil hepatic arterial infusion chemotherapy for advanced hepatocellular carcinoma. Cisplatin will be administered at a dose of 20 mg/m² on day 1 (within 30 days), and fluorouracil will be administered at a dose of 330 mg/m²/day by hepatic infusion using a reservoir for 5 days from day 1 through day 5 (continuous infusion over 24 h), followed by 2 days off. This sequence will be repeated for 2 weeks, followed by 2 weeks off. Sorafenib will be administered continuously at a dose of 400 mg twice daily for 28 days from day 1 to day 28. This 4-week period constitutes one cycle.

The first cycle of treatment will be started within 28 days of randomization. Treatment with sorafenib before hepatic arterial infusion chemotherapy will be allowed. However, patients must be off sorafenib for 2 days before and 7 days after reservoir placement. The next cycle of treatment will be started within 14 days. Sorafenib will be continued until the start of the next cycle. This combination therapy will be continued until discontinuation of the protocol treatment.

If an adverse event is observed, treatment will be interrupted or the dose will be reduced as appropriate in accordance with **6.3.2. Criteria for adjusting the sorafenib dose (dose interruption and reduction)** and **Section 6.3.3. Criteria for Hepatic Arterial Infusion Chemotherapy (Low-dose FP) Dose Adjustment (Dose Interruption and Reduction)**. After the protocol treatment is discontinued, appropriate treatment as described in **Section 6.5 Post-trial Treatment** will be instituted.

The arterial catheter should be placed in a manner that allows for proper drug distribution throughout the liver, and the flow should always be checked by contrast CT through the port or by DSA before starting treatment.

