8.5. Imaging

Lesions will be imaged by dynamic CT or dynamic MRI 4 weeks (\pm 1 week) after the start of treatment and every 8 weeks thereafter until progression is confirmed.

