12.3. Subgroup Analysis

Stratified analysis by average and total sorafenib dose will be performed.

Infusion frequency and overall survival will be compared in the arterial infusion group.

Overall survival will also be compared by baseline patient characteristics (hepatic function, age, sex, and tumor markers).

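### OS by response and by total sorafenib dose groups patients on post-randomization events but times survival from randomization, which biases both comparisons towards responders and the more exposed

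*Protocol*

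**What the plan says.** Protocol section 11.6.1 defines OS as "The length of time from the date of randomization until death from any cause". Three planned comparisons then divide patients by something observed after that date.

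- **Response.** Section 11.6.2: "OS will be compared between responders and non-responders". Section 1 lists this as a secondary endpoint. Response is judged on changes in viable tumor diameter "that are observed until completion or discontinuation of the protocol treatment" (11.6.2), and section 3.2 adds: "Determinations of the best overall response will not require confirmation".
- **Sorafenib dose.** Section 11.5: "Stratified analysis by average and total sorafenib dose will also be performed". Section 12.3 repeats this.
- **Infusions.** Section 12.3: "Infusion frequency and overall survival will be compared in the arterial infusion group". Section 11.1 says the same. Neither says whether frequency is a number or a rate.

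On timing, section 6.1.1 states: "The first cycle of treatment will be started within 28 days of randomization". Section 8.5 places the first scan 4 weeks (±1 week) after the start of treatment and later scans "every 8 weeks thereafter until progression is confirmed". Treatment is repeated until progression or another stopping criterion, and death is one of these (0.5.1, 0.5.2, 6.2). Section 11.1 names a Cox model for efficacy without a time-dependent term.

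**The concern.** A patient must be alive at a scan to be called a responder, and alive on treatment to accumulate dose or infusions. Survival before that moment is guaranteed for one group, while early deaths fall into the other. With the clock running from randomization, the guaranteed time is credited to responders and to the more heavily exposed, so they appear to live longer even if response or dose has no bearing on survival.

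Section 11.6.2 sets OS by response beside OS by Vp with nearly the same wording. Vp grade is a baseline randomization factor (5.3) and has no such problem; response does. At stake is the meaning of one listed secondary endpoint and of the exposure analyses. Their null hazard ratios can come close to the design effect of 0.59 (12.1), so an artefact of the grouping could be mistaken for a real association.

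**Working it through.** The plan gives no figure for these comparisons, so there is none to reproduce. The question is what they return when the true hazard ratio is 1.

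**Inputs from the protocol.** Median OS 10 months under control (12.1), 17 months with a 70% improvement. 190 patients, 95 per group. Enrollment 45 months and follow-up 12 months (12.2). Start within 28 days (6.1.1). Scans at weeks 4, 12, 20 and so on after the start (8.5). Phase I response rate 38.9%; TTP 9.7 months for the combination and 5.4 months for sorafenib (2.4.3), used as stand-ins for time on treatment.

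**Assumed.** When responses appear, the share of responders (20–40%), the spread of dose rates, and median splits for dose and infusion number.

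**1. Deaths before any scan.** With the latest start, the first scan is 28 + 28 = 56 days, or 56/30.44 = 1.84 months, after randomization. Deaths by then are 1 − exp(−ln 2 × 1.84/10) = 12.0%, or 7.2% with a 17-month median. All count as non-responders.

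**2. Response, by hand.** Let λ = ln 2/10 = 0.0693 per month, s the detection time, p the share who would respond if alive, and S = exp(−λs). Using deaths per person-month, without censoring:

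- responders: 1/(s + 1/λ)
- non-responders: (1 − pS)/[1/λ − pS(s + 1/λ)]

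Take p = 0.389 and a start on day 14.

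- All detected at week 4: s = 42 days = 1.38 months, S = 0.909. Rates 0.0633 and 0.0731; ratio 0.865.
- All detected at week 12: s = 98 days = 3.22 months, S = 0.800. Rates 0.0567 and 0.0771; ratio 0.735.

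**3. Response, by simulation.** With 190 patients, a 10-month median, scans at weeks 4/12 or 4/12/20 after the start and 20–40% responders, the null HR is 0.73–0.86, significant at two-sided 0.05 in 9–45% of trials. The hand calculation gives almost the same range.

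The result depends on when responses appear. With exponential times to response, groups of 95 or 190 and OS medians of 10 or 17 months, a median time to response of 0.5 month gives HR 0.80–0.85, 1.5 months gives 0.70–0.75 and 3 months gives 0.61–0.66. Those runs also counted responses first seen after treatment had stopped, which section 11.6.2 does not allow, so the larger effects are a sensitivity check only.

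**4. Total dose, by hand.** With a constant daily dose, total dose is proportional to the smaller of survival and time to discontinuation. Let M be median OS, D the median time to discontinuation and c the median of the smaller time. Then λc = ln 2 × D/(M + D), and the ratio of death rates above and below the median is (1 − λc)/(1 + λc).

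- D = 5.4: λc = 0.693 × 5.4/15.4 = 0.243; ratio 0.757/1.243 = 0.61.
- D = 9.7: λc = 0.693 × 9.7/19.7 = 0.341; ratio 0.659/1.341 = 0.49.

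Simulation with varying dose rates (190 patients, 10-month median) gives HR 0.62 and 0.51, significant at two-sided 0.05 in 84.5% and 98.7% of trials. Over all settings tried, HR was about 0.45–0.74, significant in 48–100%.

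**5. Infusions, if a number is meant.** In 95 patients with OS medians of 10 or 17 months, HR is 0.54–0.61 with D = 5.4 and 0.42–0.48 with D = 9.7.

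**6. Average dose.** Taken as a rate independent of survival: HR 1.00–1.01, with 4–4.5% rejection at one-sided 0.05.

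**7. Landmark.** Keeping patients alive at 4 months, grouped by response or exposure up to then, and timing OS from then, the null HR is 1.00–1.01 and rejection 3–6%.

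**The case against.** The strongest objection is that the protocol names no method for these comparisons. No wording excludes a landmark, a Cox model can carry a time-dependent term, and a statistical analysis plan, not available here, may settle it. That stands as a limit: plain grouping is how the text reads, not something it spells out. It does not remove the point, because the protocol does fix the groups and the clock. For whole-treatment total dose, a later plan could cure the bias only by changing the grouping variable.

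Some stronger readings are tempting but not supported.

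- *A false benefit will be shown.* The direction of bias is systematic; a significant result is not assured. For response it occurs in a minority of trials under the protocol's scan schedule.
- *Larger figures for response.* If no response could be detected before week 12, HR would fall to 0.62 with 79% of trials significant (40% responders). Section 8.5 puts the first scan at 4 weeks and section 3.2 asks for no confirmation, so a response can be recorded much earlier.
- *Infusion count is analysed.* The text says frequency. A rate would be much less affected.
- *The results will be presented as proof that more treatment prolongs life.* No section says so. The objective rests on randomized OS, and dose and infusions appear only as subgroup analyses.

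**Conclusion.** The point holds for OS by response and OS by total sorafenib dose, and for infusion frequency if it means a number. Followed as written, these comparisons favour responders and the more exposed when there is no association: HR about 0.73–0.86 for response and about 0.45–0.74 for total dose. The response range rests on the protocol's scan times and an assumed 20–40% responders; the dose range rests mainly on assumed time on treatment. The direction does not depend on these assumptions; the size does.

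Severity is moderate. A reader might infer that the trial's main conclusion is compromised. It is not: the primary OS comparison follows randomization, and sample size, conduct and data collection are unaffected.

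**What to change.** - **Sections 11.5, 11.6.2 and 12.3:** for OS by response and OS by dose, specify a landmark fixed in advance and tied to a scheduled scan. Include patients alive at the landmark, group them by response or dose accrued up to it, and time OS from it. Alternatively, enter response or accrued dose as a time-dependent covariate in the Cox model. A landmark 4 months after randomization would follow the week-12 scan even with the latest start (28 + 84 = 112 days, or 3.7 months).
- **Total dose:** do not group by whole-treatment total. Dose accrued up to the landmark is acceptable.
- **Sections 11.1 and 12.3:** define infusion frequency as a rate, or handle the number of infusions by the same landmark.
- **Reporting:** label all of these as non-randomized associations.

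The change is analysis wording and needs no new data. The cost is that deaths before the landmark leave these secondary analyses: at 4 months, 1 − 2^(−4/10) = 24% of patients with a 10-month median, or 1 − 2^(−4/17) = 15% with a 17-month median. The time-dependent version keeps them.
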